9.2. Reporting AEs/SAEs

The Investigator is to report all AEs directly observed or spontaneously reported by patients using concise medical terminology on the appropriate CRF. Each patient will be questioned about AEs at each clinic or evaluation visit, asking, for example, “Since your last clinic visit have you had any health problems?”

The AE reporting period begins with the first dose of study drug and ends with the last scheduled study evaluation or until all drug related toxicities and ongoing AEs have resolved, whichever is later.

All AEs/SAEs or exposure during pregnancy must be reported to Immunomedics or its designee, whether or not considered related to study medication using the appropriate forms/procedure. For SAEs, the Sponsor designated contact is to be notified by the Investigator, using the designated form, **within 24 hours of awareness of the event**. The initial report is to be followed by submission of more detailed SAE information within 5 calendar days of the event.

Clinical Research Department

Immunomedics, Inc.
[name]
[name]

PPD

Reporting requirements for AEs are summarized in the following table:

Table 8: Reporting Requirements for Adverse Events

	Reporting Time	Type of Report
SERIOUS	Within 24 hours	Initial report on designated SAE form
	Within 5 calendar days	Follow-up/Final report on designated form
NON-SERIOUS	Per CRF submission procedure	Appropriate CRF pages

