A single whole-blood sample (purple- or pink-topped tube, 2 mL) will be collected from each registered patient prior to receiving IMMU-132 for determination of UGT1A1 and related genotypes. This sample will be shipped to Sponsor who will perform this assay. The results from this test are NOT required to determine eligibility but will be used retrospectively to assess its utility in predicting toxicity.

 PPD

 Core biopsies that are  fresh-frozen and also formalin-fixed (described above) are also desired at baseline and intervals during therapy whenever possible.

In the ongoing Phase II study, all patients receive IMMU-132 10 mg/kg administered in 3-week treatment cycles with weekly dosing the first two weeks (days 1 and 8 of 21-day cycles) and no dosing the third week. The cycles are to be continued in the absence of unacceptable toxicity or progression of disease requiring termination of further treatment. The first assessment of disease progression per RECIST1.1 does not require discontinuation of study treatment if there is still the potential for patient benefit in the opinion of the investigator and approved by the Sponsor, but treatment must be discontinued if subsequent imaging documents disease progression from that assessment.

All patients are closely monitored over the course of their treatment, and NCI CTCAE v4.0 is used to grade all adverse events and to provide dose reduction, delay or cessation guidelines in the event of treatment-related toxicity. Based on irinotecan and animal testing, the major toxicity of IMMU-132 is expected to be gastrointestinal symptoms and hematologic suppression. Growth factors and other supportive care are allowed when medically necessary any time during treatment with IMMU-132 but should not be given prophylactically before start of treatment with IMMU-132 first dose in cycle 1.

In the current experience in over 200 patients, the major Grade 3 or Grade 4 toxicity has been neutropenia, which is managed with dose delay, dose reduction, or growth factors, if spontaneous remission is not experienced within 7 days.

CCI

CCI

Patients who exhibit an excessive cholinergic response to IMMU-132 treatment (e.g., abdominal cramping, diarrhea, salivation, etc.) can receive appropriate premedication (e.g., atropine) for subsequent treatments.

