6.1. Informed Consent

No study procedure or alteration of patient care will be undertaken until informed consent has been obtained from the patient or legal representative. The Investigator will explain the nature and scope of the study, potential risks and benefits of participation, and answer questions for the patient and/or legally authorized representative.

A table of approved or standard therapeutic regimens for each of these cancer types is included in [Appendix 1](#). *Patients who have not received all approved or standard treatment lines for their cancer must be informed that these alternatives to receiving IMMU-132 are available prior to consenting to participate in this trial.*

If the patient agrees to participate, the informed consent form will be signed, dated, and witnessed, with a copy given to the subject.

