7.4.7. Biopsy specimens

At the discretion of treating physician, patients who have biopsiable lesion(s) and consented to biopsy(ies) will provide before and during the study as many tumor metastasis core biopsy samples (~0.2 to 0.5 cm³) as possible.

Procedure for Handling Core Biopsies

Samples should be shipped to Immunomedics to perform research assays intended to detect a variety of biomarkers, CCI. The purpose of this testing is to develop a database that will be used to assess biomarker status versus anti-tumor response to IMMU-132. Immunomedics recommends investigators participating in the collection of core biopsy samples consult with their institutional Pathology Department for the processing and handling of specimens. While some of the testing can be performed on conventionally preserved specimens (i.e., fixed in 10% buffered formalin), other assays require fresh tissue that should be snap frozen in liquid nitrogen or another suitable method typically used by Pathology Departments to prepare frozen tissues for RNA, protein, and microscopic examination. Thus, Immunomedics is requesting both formalin-fixed and fresh/frozen tissues according to the procedure described below:

If possible, obtain 4-6 core biopsy samples from sites of confirmed cancer. If 4 cores are obtained, 2 should be placed in 10% buffered formalin, the other 2 should be flash frozen (6 cores, split 3+3; 2 cores, split 1+1; odd number cores, process more by flash freezing).

- a. 10% buffered formalin: Place specimens in suitable leak-free container. Add enough formalin to cover completely. Ensure specimen is completely immersed. Sample can be stored at room temperature or in refrigerator prior to shipping. Sample should remain in the fixative at least overnight before shipping. When shipping, the vessel containing the tissue should be filled with formalin as much as possible so that tissue will remain in contact with the formalin.
- b. Flash-frozen: Tissues processed in this manner are best handled by the Pathology/Histology department. The core biopsies should be placed in a small amount of saline to transport. The tissue is then gently blotted dry, placed in a cassette containing a small amount of a cryoprotective embedding media (e.g., OCT compound). The cassette is then partially filled with this compound to cover tissue and then snap-frozen using a freezing spray or liquid nitrogen. Ship to Immunomedics frozen on dry ice.

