9.3. Recording Information on AEs

All AEs, whether observed by the Investigator, elicited from, or volunteered by the patient, will be recorded including: duration, severity, relationship to the study medication, treatment, action taken with respect to the study medication and outcome. When possible, all events should be reported in diagnostic terms or the most acceptable medical terms in order to interpret safety information accurately.

The investigator must review all laboratory and test data and record any adverse events. The same format will be used as for other adverse events, regardless whether related to study therapy or not, including event severity grading, attribution, and resolution. A summary listing of all adverse events occurring during the past year on this study will be provided in progress reports reported to regulatory authorities.

The investigator will notify Immunomedics or its designee if he/she becomes aware at any time, during or following the study, of the occurrence of death or new malignancy involving the participant of a clinical trial, even though the event may not appear to be drug related.

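### Adverse event reporting opens at first dose, so non-fatal serious complications of optional pre-dose research biopsies need not reach the sponsor and are absent from the trial's AE summaries

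*Protocol*

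**What the plan says.** **Reporting window.** Protocol 9.2 says "The AE reporting period begins with the first dose of study drug". In the Study Calendar (Table 2) the adverse event row is blank in the pretreatment column and first marked at Cycle 1 Day 1. Within that window the scope is wide: "All AEs/SAEs or exposure during pregnancy must be reported to Immunomedics or its designee, whether or not considered related to study medication".

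**Pre-dose biopsies.** Protocol 7.4.7 says that patients with a biopsiable lesion who consent, at the treating physician's discretion, "will provide before and during the study as many tumor metastasis core biopsy samples" as can be obtained. It adds: "If possible, obtain 4-6 core biopsy samples from sites of confirmed cancer". The purpose is research: "Samples should be shipped to Immunomedics to perform research assays intended to detect a variety of biomarkers". The Synopsis says that core biopsies "are also desired at baseline and intervals during therapy whenever possible".

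**Consent.** Protocol 6.1 says "No study procedure or alteration of patient care will be undertaken until informed consent has been obtained". Section 6.3 allows up to 4 weeks for baseline evaluations.

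**Exceptions and parallel duties.** Under Protocol 9.3 the investigator must tell the sponsor, at any time, "of the occurrence of death or new malignancy involving the participant of a clinical trial". Protocol 14.2 makes the investigator responsible for notifying the IRB/IEC of every SAE at the site and gives no start date.

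**Analysis.** SAP 7.1 lists all AEs but summarizes only those with onset or worsening from the start of study drug to 30 days past the last dose. SAP section 5 leaves patients who were entered but not dosed out of all analyses.

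**The concern.** A core biopsy taken for sponsor assays is an invasive act done for the study. Its risk falls on the patient from the moment of the procedure, whether or not study drug follows. With the reporting period tied to first dose, a consented patient could be hospitalized with a bleed, a pneumothorax or an infection after a baseline biopsy without any duty on the site to tell the sponsor. If the complication also prevents dosing, the patient drops out of the analysis sets.

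What is at stake is the sponsor's ability to weigh the harm of a procedure that it requests. Efficacy estimates and treatment-emergent safety tables are not affected.

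**Working it through.** The plan states no figure to reproduce and no arithmetic applies. The check follows a serious complication of a pre-dose biopsy through each rule.

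1. *Can the biopsy fall on study but before reporting opens?* Yes. Consent must come before any study procedure (6.1), baseline may run up to 4 weeks (6.3), and the biopsy is requested in that interval (7.4.7, Synopsis). Reporting opens only at first dose (9.2, Table 2).

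2. *Could archival tissue make the fresh biopsy unnecessary?* Only in part. Appendix 6 accepts archival paraffin tissue for tissue testing, but 7.4.7 says that some assays need fresh, snap-frozen tissue.

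3. *Does another rule bring the event to the sponsor?*

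| Course of the pre-dose complication | Required report to the sponsor | Place in the SAP |
|---|---|---|
| Death or new malignancy | Yes (9.3, at any time) | None if never dosed |
| Worsens after dose 1 | Yes (section 9 counts worsening of a pre-existing condition; 9.2) | Treatment-emergent AE (7.1) |
| Otherwise non-fatal, patient then dosed | None stated | Not in AE summaries; may appear as medical history (5.4.1) |
| Otherwise non-fatal, patient never dosed | None stated | Excluded from all analyses (section 5) |

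The last two rows are the gap.

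4. *Is causality to a study procedure asked for?* No. Sections 9 and 9.3 ask for the relationship to study drug or study medication only. Even a complication that a site chose to report would have no stated place for attribution to the biopsy.

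5. *Does the ethics committee hear of it?* On a literal reading of 14.2, yes, in every row of the table. That duty runs from site to committee and does not place the event in the sponsor's database. Sections 9.2 and 14.2 therefore have different starting points, and neither refers to the other.

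6. *How many events?* This cannot be derived. The documents give no count of baseline research biopsies and no complication rate, and part of the biopsy text is redacted.

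**The case against.** Starting AE collection at first dose is a legitimate design choice for describing the drug, and the biopsies are optional, so exposure may be small. Both statements are true. They limit the size of the gap but do not remove the reason to track harm from a procedure requested for research.

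A reader might infer that these complications are never reported, that ethics committees cannot see them, or that nothing is captured unless the patient dies. The documents do not support any of these readings. Section 14.2, taken literally, sends the SAE to the IRB/IEC. Section 9.3 covers new malignancy as well as death. Section 9 and SAP 7.1 pick up a complication that worsens after dosing starts. For dosed patients the event may also be noted in the baseline medical history, although not as an SAE and not attributed to the biopsy. Nor do the documents support an expected number of missed events, since both inputs would have to be assumed.

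The strongest practical objection is timing. SAP 3.3 puts the last enrollment at 22 June 2017, SAP section 4 plans a data cut-off of 1 March 2019, and the protocol revision is dated 23 January 2020. Unless enrollment reopened, nobody remains between consent and first dose, and new wording in 9.2 would capture no further patient here. This stands, and it shapes the fix.

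**Conclusion.** The point holds as a gap in reporting to the sponsor and in the trial's AE summaries. It covers non-fatal serious complications of optional pre-dose research biopsies, other than new malignancy and events that worsen after dose 1. It is widest for patients biopsied but never dosed, who are outside every SAP analysis. The mismatch between 9.2 and 14.2 is part of the same defect.

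The size is unknown and may be small. No efficacy result or treatment-emergent table changes.

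The conclusion rests on two assumptions. The first is that no redacted text qualifies 9.2; the sentence itself is intact and unqualified. The second is that the published wording also applied while patients were being enrolled. The protocol under review includes Amendments 1 to 13, whereas the SAP cites the version of 24 April 2017 with Amendments 1 to 11, which is not available here.

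**What to change.** - **Protocol 9.2 and Table 2:** require reporting to the sponsor, from signed consent, of SAEs related to study-specific procedures, naming optional research biopsies. A phrase limited to required procedures could miss them. Keep full AE collection from first dose, and ask for the relationship to study procedure for these events.
- **Protocol 14.2:** state the same starting point, or say explicitly that the duty to the IRB/IEC begins at consent, so that it agrees with 9.2.
- **SAP:** add a separate listing of pre-dose SAEs related to study procedures, including patients never dosed, as a stated exception to the exclusion in section 5. Leave the TEAE definition and tables as they are.
- **Data already collected:** send sites a targeted query limited to serious complications of baseline research biopsies, including those in patients who were not then dosed. State in the CSR that pre-dose procedure-related SAEs were not prospectively collected.

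The cost is modest site and data-management work. The query is the larger part: it goes to many centers, may reach back toward the protocol's 2012 release, and concerns some patients for whom AE reporting never opened. With enrollment closed, the protocol wording mainly corrects the rule for the record and for protocols derived from this one. The query and the listing are what can still recover information.

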9.3. Recording Information on AEs

All AEs, whether observed by the Investigator, elicited from, or volunteered by the patient, will be recorded including: duration, severity, relationship to the study medication, treatment, action taken with respect to the study medication and outcome. When possible, all events should be reported in diagnostic terms or the most acceptable medical terms in order to interpret safety information accurately.

The investigator must review all laboratory and test data and record any adverse events. The same format will be used as for other adverse events, regardless whether related to study therapy or not, including event severity grading, attribution, and resolution. A summary listing of all adverse events occurring during the past year on this study will be provided in progress reports reported to regulatory authorities.

The investigator will notify Immunomedics or its designee if he/she becomes aware at any time, during or following the study, of the occurrence of death or new malignancy involving the participant of a clinical trial, even though the event may not appear to be drug related.

9.4. Grading of AE Severity

The severity of AEs will be graded using the CTCAE Version 4.0. For each event, the highest severity grade should be reported. If a CTCAE criterion does not exist, the Investigator should use the grade or adjectives as described in [Table 9](#).

Table 9: Grading of Adverse Event Severity

Grade	Adjective	Description
Grade 1	Mild	Does not interfere with patient's usual function
Grade 2	Moderate	Interferes to some extent with patient's usual function
Grade 3	Severe	Interferes significantly with patient's usual function
Grade 4	Life-Threatening	Results in a threat to life or in an incapacitating disability

A severe reaction (e.g., a severe headache) would not be classified as serious unless it met one of the criteria for SAE(s) listed above.

9.5. Pregnancy

The Sponsor must be notified of any patient or partner of a male patient becoming pregnant during the study, and any pregnancy must be followed until completion or termination of pregnancy. In the case of a live birth, the “normality” of the newborn can be assessed at the time of birth. The “normality” of an aborted fetus can be assessed by gross visual inspection unless pre-abortion laboratory findings are suggestive of a congenital anomaly.

9.6. Follow-up of Unresolved AEs

All AEs should be followed until they are resolved, or the Investigator assesses them as chronic or stable or the patient's participation in the trial ends (i.e., until a final report is completed for that patient). Instructions for reporting changes in an ongoing AE during a patient's participation in the trial are provided in the instructions that accompany the AE CRFs.

In addition, all AEs and SAEs assessed by the Investigator as possibly related to the investigational medication/product should continue to be followed even after the patient's participation in the trial is over. Such events should be followed until they resolve or until the Investigator assesses them as “chronic” or “stable.” Resolution of such events is to be documented on the appropriate CRF.

10. STATISTICAL CONSIDERATIONS

10.1. Overview and Study Design

This is an open label, non-randomized Phase I/II study in patients with a variety of refractory/relapsed metastatic epithelial cancers. Prior use of irinotecan or other camptothecin-derived agents (e.g., topotecan) is allowed except when there is a known history of anaphylactic reaction or \geq Grade 3 GI toxicity to prior irinotecan. The primary objectives of Phase I are to evaluate the safety and tolerability of several dose levels of the antibody-drug conjugate IMMU-132 (hRS7-SN-38). The secondary objectives are to obtain preliminary information on efficacy, pharmacokinetics, and immunogenicity. The primary objective in Phase II is the evaluation of the safety and efficacy of IMMU-132 administered in 3-week treatment cycles, at a dose selected in Phase I; secondary objectives also include pharmacokinetics and immunogenicity.

The dose escalating phase has been completed and 12 mg/kg (on Days 1 and 8 of a 21-day cycle identified as the MTD. The Phase II expansion is ongoing at 10 mg/kg dose level, including enrollment currently focusing on 5 expansion cohorts (TNBC, non-TNBC, NSCLC, SCLC, UC).

CCI

10.3. Safety Analysis

In general, all patients administered any dose of study drug will be included in the evaluation of safety.

Dose escalation continued for determination of the MTD, but for the Phase II portion of the protocol, the Sponsor will select 2 dose levels; one where at least 2 of 6 patients can complete the first cycle without \geq Grade 3 toxicity and the other a lower dose level.

The frequency and severity of adverse events (AEs) will be tabulated by MedDRA Preferred Term and System Organ Class (SOC) for each dose group. AEs will be classified using the MedDRA version 10 with severity assessed by NCI CTCAE v4 toxicity grades. The frequency of AEs will be tabulated by MedDRA System Organ Class (SOC) and Preferred Term for each dose group. For this purpose, an AE that occurs more than once within each patient will be counted only once (at the worst CTCAE grade and relationship category). In the same fashion, similar AEs will be consolidated using the worst CTCAE grade and relationship category observed prior to classification into each MedDRA SOC.

AEs leading to death or to discontinuation from treatment, as well as all SAEs will be summarized separately, if appropriate. The reasons for discontinuation will also be summarized for each dose group using frequency distributions.

Both actual and change-from-baseline data on vital signs will be summarized using descriptive statistics by dose group for each study time-point.

Routine safety laboratories, based on hematology and serum chemistry data, will be listed by patient and summarized by descriptive statistics for each dose group, if appropriate. Laboratory test results will be graded according to CTCAE severity grade when applicable. The frequency distribution of the worst CTCAE grade observed will be tabulated in a shift table for each parameter by dose group.

Similarly, data on human anti-hRS7 antibody responses (HAHA) will be listed and summarized by descriptive statistics, if appropriate. In addition, PK data documenting the clearance of SN-38 in a select number of patients will be used to gain preliminary information on the conjugate's clearance properties, focusing on the area under the curve for total SN-38 (IgG-bound and free) and free SN-38. This value potentially could be helpful for assessing toxicity.

Furthermore, the UGT1A1 genotype will be determined at baseline and compared to hematological toxicity.

10.4. Efficacy Analysis

In general, all patients who were treated with at least one complete cycle of study drug and have available response assessment data will constitute the efficacy population and be included in the analysis of efficacy.

The objective response rate (ORR) and duration of response, will be tabulated and summarized by descriptive statistics for patients in each indication. Progression-free survival (PFS) and overall survival (OS) will be summarized, either by tabulation, or, if feasible, by Kaplan-Meier methodology. Other efficacy analysis may be performed as appropriate.

